6.3. Analysis for Secondary Endpoints

6.3.1. Efficacy Endpoints Analysis

ORR, as assessed using PCWG2 for prostate cancer and RECIST version 1.1 for other tumor types, is a key efficacy endpoint. The following analyses will be performed in the mITT population by tumor type and pooled:

The ORR, along with other efficacy analyses will be performed in the mITT population. Part 1 and Part 2 data will be summarized separately, and may also be pooled together for analysis if deemed necessary. Specifically, the key tables in Part 2 include:

1. ORR by visit: investigator provided tumor response CR, PR, and CR+PR will be presented by descriptive statistics (frequency and percentage) and 95% confidence interval.
2. Best overall response of CR, PR, and CR+PR. This will include best overall response derivation without confirmation and with confirmation. Descriptive statistics (frequency and percentage) and 95% confidence interval will be provided.

Tumor response data in Part 1, Part 2 and across the two Parts may be summarized with descriptive statistics (frequency and percentage) in the following groups by visit and then best overall response across all visits:

- Overall summary for all doses and all tumor types;
- By tumor type regardless of dose;
- By dose regardless of tumor type;
- By dose and tumor type if data permit.

Summary tables of best overall response rate, PFS, OS, DOSD, and DOR may be provided by the groups aforementioned when deemed necessary (eg, if there are ≥ 5 patients in a specific group).

In addition, PSA50 Response Rate defined as $\geq 50\%$ PSA reduction from baseline assessed by PCWG2 for prostate cancer patients will be summarized similarly as ORR. See [Section 9.5](#) for more details on PSA measurement.

Efficacy listings (tumor measurements listings and tumor response listings) will be provided that include the investigator provided tumor measurement data, tumor response, best overall response, first CR/PR date, last date with CR or PR, most recent date without progression, progression date, death date, and last tumor assessment date, etc.

Endpoint	Analysis Set	Statistical Method	Model/Covariates/Strata	Missing Data
Overall response	mITT	Exact CI	See aforementioned summary descriptions on data pooling across dose and tumor type	Observed case
Overall Survival	ITT	Kaplan-Meier	See aforementioned summary descriptions on data pooling across dose and tumor type	Censored at last visit
Progression Free Survival (PFS)	mITT	Kaplan-Meier	See aforementioned summary descriptions on data pooling 3721 across dose and tumor type	Censored per Section 9.2
Time to Progression (TTP) and Time to Response (TTR)	mITT	Kaplan-Meier	See aforementioned summary descriptions on data pooling across dose and tumor type	Censored per Section 9.2
Duration of Response (DOR)	mITT	Kaplan-Meier	See aforementioned summary descriptions on data pooling across dose and tumor type	Censored per Section 9.2

Swimmer plot for individual clinical response and time on treatment, waterfall plot for individual tumor size percent change from baseline, and spider plot for individual tumor size percent change from baseline over time may be presented if needed. The following table provides an overview of the efficacy analysis if the data is sufficient.

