6.4. Patient Withdrawal

Withdrawal of Consent:

Patients who request to discontinue receipt of study treatment will remain in the study and must continue to be followed for protocol specified follow-up procedures. The only exception to this is when a patient specifically withdraws consent for any further contact with him or her or persons previously authorized by the patient to provide this information. Patients should notify the investigator in writing of the decision to withdraw consent from future follow-up, whenever possible. The withdrawal of consent should be explained in detail in the medical records by the investigator, as to whether the withdrawal is only from further receipt of investigational product or also from study procedures and/or posttreatment study follow-up, and entered on the appropriate CRF page. In the event that vital status (whether the patient is alive or dead) is being measured, publicly available information should be used to determine vital status only as appropriately directed in accordance with local law.

Lost to Follow-Up:

All reasonable efforts must be made to locate patients to determine and report their ongoing status. This includes follow-up with persons authorized by the patient as noted above. Lost to follow-up is defined by the inability to reach the patient after a minimum of 2 documented phone calls, faxes, or e-mails as well as lack of response by the patient to 1 registered mail letter. All attempts should be documented in the patient's medical records. If it is determined that the patient has died, the site will use locally permissible methods to obtain the date and cause of death. If the investigator's use of a third-party representative to assist in the follow-up portion of the study has been included in the patient's informed consent, then the investigator may use a sponsor-retained third-party representative to assist site staff with obtaining the patient's contact information or other public vital status data necessary to complete the follow-up portion of the study. The site staff and representative will consult publicly available sources, such as public health registries and databases, in order to obtain updated contact information. If, after all attempts, the patient remains lost to follow-up, then the last-known-alive date as determined by the investigator should be reported and documented in the patient's medical records.

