4.4. Modified Intent to Treat (mITT) Population

The modified intent to treat (mITT) is the analysis population that will follow the ITT principle and include patients receiving at least 1 dose of investigational product with baseline assessment and at least 1 post baseline assessment, disease progression, or death before the first tumor assessment. The mITT population will be used for analyses and to support conference presentations when the study is still ongoing.

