5.3.1. Analyses for Time to Event Data

Time to event endpoints in this study may include progression-free survival (PFS), duration of response (DOR), time to response (TTR), time to progression (TTP), and overall survival (OS). These endpoints will be summarized using the Kaplan-Meier method⁶ and displayed graphically when appropriate. Median event times and 2-sided 95% confidence intervals for time-to-event endpoint (Brookmeyer and Crowley, 1982)⁷ will be provided.

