5.4. Methods to Manage Missing Data

5.4.1. Missing Dates

In compliance with Pfizer standards, if the day of the month is missing for any date used in a calculation, the 1st of the month will be used to replace the missing date unless the calculation results in a negative time duration (eg, date of onset cannot be prior to day one date). In this case, the date resulting in 0 time duration will be used. Pfizer standards are also used if both month and day are missing (Jan 1 unless negative time duration). This excludes the pharmacokinetic, ECG, **CCI** analyses, which will only use the actual date collected or if date not available deem the data missing.

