5.4.2. Efficacy Analysis

For the time-to-event endpoints, the missing data handling method will be censoring. Censoring rules for time-to-event endpoints are detailed in [Section 9.2](#).

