9.2. Time to Event Data Analysis Censoring Rules

Table 1. Progression Free Survival and Duration of Response

Situation	Date of Progression/Censoring¹	Outcome
Inadequate baseline assessment	First dosing date in Cycle 1	Censored
No on-study assessments	First dosing date in Cycle 1	Censored
Alive, on treatment ² and no Progression	Date of last objective tumor assessment	Censored
Progression Documented on or between scheduled tumor assessments prior to treatment discontinuation ²	Date of first objective tumor assessment showing objective progression	Progressed (Event)
Treatment discontinuation for undocumented progression	Date of last objective tumor assessment prior to discontinuation ²	Censored
Treatment discontinuation due to toxicity or other reason	Date of last objective tumor assessment prior to discontinuation ²	Censored
Death prior to first planned tumor assessment	Date of death	Death (Event)
Death without objective progression prior to treatment discontinuation ²	Date of death	Death (Event)
Death or progression after 2 or more missed tumor assessments	Date of last objective tumor assessment prior to the event	Censored

1. For date of censorship, if a tumor assessment takes place over a number of days (eg, superficial lesions one day, scans another), the last date is used as the assessment date.

2. Or within 28 days of discontinuation of treatment.

Table 2. Time to Progression

Situation	Date of Progression/Censoring¹	Outcome
Inadequate baseline assessment	First dosing date in Cycle 1	Censored
No on-study assessments	First dosing date in Cycle 1	Censored
Alive, on treatment ² and no Progression	Date of last objective tumor assessment	Censored
Progression Documented on or between scheduled tumor assessments prior to treatment discontinuation ²	Date of first objective tumor assessment showing objective progression	Progressed (Event)
Treatment discontinuation for undocumented progression	Date of last objective tumor assessment prior to discontinuation ²	Censored

Table 2. Time to Progression

Situation	Date of Progression/Censoring¹	Outcome
Treatment discontinuation due to toxicity or other reason	Date of last objective tumor assessment prior to discontinuation ²	Censored
New anticancer treatment <28 days after discontinuation of treatment without progression	Date of last objective tumor assessment prior to new anticancer treatment	Censored
Death prior to first planned tumor assessment	Start date (C1D1)	Censored

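### A partial death date can be imputed to before the patient was last known alive, and time to response is sent to a censoring section that has no rule for it

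*SAP*

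**What the plan says.** **Dates.** SAP 5.4.1 covers any date that enters a calculation. If the day is missing, "the 1st of the month will be used to replace the missing date unless the calculation results in a negative time duration"; in that case the date giving zero duration is used. If month and day are both missing, 1 January is used with the same guard. The PK and ECG analyses and one redacted analysis are exempt. Death dates are not. OS is analysed by Kaplan-Meier in the ITT set (SAP 6.3.1), and Table 1 of SAP 9.2 counts death as a PFS event. Protocol 9.3 lists both the death date and the date of last contact. Protocol 6.4 has survival followed by telephone every 8 weeks.

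**Time to response.** In the SAP 6.3.1 table the row for "Time to Progression (TTP) and Time to Response (TTR") gives the analysis set as mITT, the method as Kaplan-Meier, and refers to Section 9.2 for censoring. SAP 5.3.1 names TTR alongside PFS, DOR, TTP and OS and says "These endpoints will be summarized using the Kaplan-Meier method", with medians and 95% confidence intervals. The mITT population of SAP 4.4 will "include patients receiving at least 1 dose of investigational product with baseline assessment and at least 1 post baseline assessment, disease progression, or death", where the death came ahead of any scan, so it is not limited to responders. SAP 5.4.2 adds: "For the time-to-event endpoints, the missing data handling method will be censoring". Section 9.2 consists of "Table 1. Progression Free Survival and Duration of Response", "Table 2. Time to Progression" and a closing line that ties DOR to PFS. SAP 9.1 defines DLT, MTD and RP2D, but not TTR.

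**The concern.** The date rule moves every partial death date to the earliest day it could be. Its guard compares only with the start of the interval, so it does nothing about later evidence that the patient was alive. The error runs in one direction: survival is shortened, and some records will contradict themselves.

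For TTR, the cross-reference leads to no rule, so the programmer must choose one. Kaplan-Meier treats a censored patient as still able to have the event. A patient who has died cannot respond, and one who has progressed is very unlikely to. If such patients are censored, their weight passes to those still on study, 1-KM exceeds the proportion who respond, and a median TTR can appear although fewer than half respond.

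TTR and OS are named secondary endpoints of Parts 2A and 2B, with 10 and 20 patients. In groups of that size a few misdated or miscensored patients can move a median.

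**Working it through.** The documents give no figure for either rule, so there is none to reproduce.

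**1. Death dates**

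Inputs: the imputation rule (SAP 5.4.1) and 8-weekly contact (Protocol 6.4). Assumptions: deaths are spread evenly over the calendar, and the last contact falls uniformly over the 56 days up to death (0 to 55 days before it).

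- *Day missing.* The loss is (day of month − 1). Over a 365-day year the mean is (7×465 + 4×435 + 378)/365 = 5373/365 = 14.7 days, and the maximum is 30.
- *Imputed date before last known alive.* This happens when the gap from last contact to death is shorter than the loss. The probability is 14.72/56 = 26% of partial dates. With 4-weekly contact it is about 52%.
- *Month and day missing.* The mean loss is 364/2 = 182 days and the maximum is 364. The imputed date precedes last known alive in about 92% of cases with 8-weekly contact and 96% with 4-weekly contact.

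Example: first dose 15 March, last known alive 21 June, death recorded as June of the same year with no day. The rule gives 1 June, so OS is 78 days. The patient was alive at day 98. The true value lies between 99 days (22 June) and 107 days (30 June). The negative-duration guard is not triggered, because 1 June is after 15 March.

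With a floor at the day after last known alive, the example gives 99 days. Under the same assumptions the floor removes every date that precedes a known contact. The mean loss with the day missing falls only from 14.7 to 11.7 days, because the 1st still applies when the last contact was in an earlier month. With month and day missing it falls from 182 to about 25 days.

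**2. Time to response**

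Inputs: the planning example of 7 responders in 16 (SAP 5.2.3) and 8-weekly scans (Protocol 7.8). The response and censoring times below are assumptions. Events are taken before censorings at tied times.

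*Pattern A.* At Week 8, 5 of 16 respond and 6 progress and are censored. At Week 16, 2 of the remaining 5 respond.

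- 1-KM = 1 − (11/16)(3/5) = 1 − 0.4125 = 58.75%.
- Proportion responding = 7/16 = 43.75%.
- The survival curve falls below 0.5 at Week 16, so a 16-week median TTR would be reported although fewer than half respond.

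*Other patterns.* Responses are at Weeks 8 (4), 16 (2) and 24 (1); the responder-only median is 8 weeks.

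| 9 non-responders | 1-KM | KM median |
|---|---|---|
| Censored 4/3/2 at Weeks 8/16/32 | 1 − (12/16)(6/8)(2/3) = 62.5% | 24 weeks |
| Censored 5/3/1 at Weeks 8/16/24 | 1 − (12/16)(5/7)(1/2) = 73.2% | 24 weeks |
| All censored at Week 8 | 1 − (12/16)(1/3)(0) = 100% | 16 weeks |
| Kept at risk to end of follow-up | 43.75% | not reached |

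The last row shows that the size of the error depends on the rule that is missing.

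*Which rule would be used?* TTR shares its row with TTP, so Table 2 is the nearest candidate. With response as the event, Table 2 censors deaths at C1D1 or at the last tumor assessment. Its progression row makes progression the event, which cannot apply to TTR, so a progressor would most naturally be censored at a scan. No row in Section 9.2 keeps a patient without an event at risk to the end of follow-up.

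**The case against.** **On TTR.** A reader might infer that the SAP states that non-responders are censored in the TTR analysis. It does not. That reading combines Kaplan-Meier, the general sentence in 5.4.2 and the shared TTP row; no TTR rule or censoring time is written, and one admissible choice gives exactly 43.75%. This stands, so the overstatement is conditional.

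The mITT entry may also name only the source population. DOR has the same mITT and Kaplan-Meier entry, yet can exist only in responders. That is fair, and it means DOR cannot be cited as a model that the SAP already handles correctly.

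Response probability is reported separately, as ORR with an exact interval, so nobody needs to read it from 1-KM. This stands as well. What remains exposed is the median TTR, which SAP 5.3.1 does ask for. Even that need not appear: with 20 patients, 5 responders and 7 progressors at Week 8 and 2 responders among 8 at risk at Week 16, 1-KM is 1 − (15/20)(6/8) = 43.75% against 7/20 = 35%, and no median is reached.

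**On dates.** Nothing says how many death dates will be partial, and Protocol 6.4 tells sites to obtain the date of death. The effect on the OS median therefore cannot be sized. Protocol 6.4 also says that "the last-known-alive date as determined by the investigator should be reported and documented", but only for patients who remain lost to follow-up. The more general source is the date of last contact in Protocol 9.3.

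A reader might also infer that a partial new-therapy date would turn a TTP event into a censoring. The documents do not establish that. The new-treatment row of Table 2 is limited to patients without progression, a separate row counts documented progression up to 28 days after discontinuation as an event, and no order of precedence is given.

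**On stakes.** There are no hypotheses (SAP 5.1), and these summaries are descriptive and made if data suffice.

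**Conclusion.** The date defect holds as written. SAP 5.4.1 applies to death dates, and its guard does not stop an imputed death from preceding a known contact. OS, and PFS when death is the event, can only be shortened. Per partial date the mean loss is about 15 days with the day missing and about half a year with the month missing too. About 26% of day-missing dates would precede last known alive, given uniform deaths and 8-weekly contact. It would go too far to say that OS will contain impossible dates, because that requires partial death dates and their number is unknown. Nor would the floor recover the whole early bias.

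The TTR defect is a dead cross-reference and an undefined risk set. It misleads if non-responders are censored at progression, death or last scan, which is the natural reading of the shared row but not a stated rule. In that case 1-KM at a 7/16 response rate ranges from 58.75% to 100% over the assumed timings.

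Both points concern descriptive secondary endpoints and do not touch the primary analyses. They are worth correcting before database release because the correction is simple.

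**What to change.** - **SAP 5.4.1:** add an exception for death. Impute a partial death date as the later of the first day of the known month or year and the day after the last date known alive, taken from the date of last contact. Where that would fall outside the known period, query the site. Say in the SAP that the rule removes impossible dates but leaves some early bias, and report the number of imputed death dates.
- **SAP 9.1 and 6.3.1:** define TTR (start date, event, confirmed or unconfirmed response). Either summarise it in responders only, with median and range, or estimate cumulative incidence of response in mITT with progression and death as competing events. Remove the reference to Section 9.2 for TTR, or add the rule there.
- **SAP 6.3.1, DOR row:** state that DOR is analysed in responders only.

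The cost is a few SAP sentences and minor programming. No design change is needed, and Protocol 9.3 already lists the date of last contact.

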6.3.2. Pharmacokinetics Analyses

The concentration-time data of PF-06952229 will be summarized by descriptive statistics (n, mean, standard deviation, coefficient of variation, median, minimum, maximum, and geometric mean) according to dosing cohort and time for each part of the study. In addition, the concentration-time data from Part 2 dose expansion will also be summarized by descriptive statistics according to tumor type.

The actual time of sample collection will be used in PK parameter calculation. In the event that the actual sampling time is not available, the nominal time may be used if there is no evidence that the actual sampling time deviates substantially from the nominal time.

Presentation of PF- PF-06952229 concentration-time data

The concentration-time data of PF-06952229 will be presented as below:

- a listing of all concentrations by cohort, subject ID and nominal time. The concentration listing will also include the actual times. Deviations from the nominal time will be given in a separate listing.
- a summary of concentrations by cohort and nominal time, where the summary statistics will include n, mean, standard deviation, median, coefficient of variation (cv), minimum, maximum and the number of concentrations above the lower limit of quantification.
- for the concentration-time data after the 1st (C1D1) and 7th dose (C1D7), median concentration-time plots (on both linear and semi-log scales) against nominal time postdose by cohort (all cohorts on the same plot per scale, based on the summary of concentrations by cohort and time postdose).

For drug concentration summary statistics, median and mean plots by sampling time, the nominal PK sampling time will be used; for individual subject plots by time, the actual PK sampling time will be used, with the pre-dose time set to zero.

Calculation of PF-06952229 PK parameters

For patients enrolled in the dose escalation stage of the study, the individual concentration-time data of PF-06952229 during Cycle 1 and Cycle 2 will be analyzed separately by non-compartmental methods to estimate the PK parameters. The PK parameters estimated will include C_{max} , T_{max} , and AUC_{last} (AUC_{tau} at steady state). If data permit or if considered appropriate, $t_{1/2}$, CL/F , V_d/F (or V_{ss}/F at steady state), and accumulation ratio (R_{ac}) will also be estimated. The PK parameters will be summarized descriptively by dose level and cycle.

Additionally, for Part 1, dose-normalized AUC_{last} and C_{max} will be plotted against dose (using a logarithmic scale) by cycle. These plots will include individual patient values and the geometric means for each dose. These plots will be used to help understand the relationship between the PK parameters and dose.

For patients enrolled in Part 2 of the study, trough concentrations of PF-06952229 will be summarized descriptively by cycle and by tumor type.

PK parameters will be calculated using standard non-compartmental methods:

Parameter	State	Method of Determination
AUC _{tau}	sd, ss	Linear/Log trapezoidal method
AUC _{last}	sd,ss	Linear/Log trapezoidal method
AUC _{inf} ^a	sd	AUClast + (C _{last} */k _{el}), where C _{last} * is the predicted serum concentration at the last quantifiable time point estimated from the log-linear regression analysis.
C _{max}	sd, ss	Observed directly from data
T _{max}	sd, ss	Observed directly from data as time of first occurrence
CL/F	sd, ss	Dose/AUC _{inf} for sd ^a Dose/AUC _{tau} for ss
Vd/F	sd, ss	Dose/(AUC _{inf} * k _{el}) for sd Dose/(AUC _{tau} * k _{el}) for ss
V _{ss} /F ^a	sd, ss	CL * MRT, where MRT is the mean residence time adjusted for the duration of infusion
t _{1/2} ^a	sd	Log(2)/k _{el} , where k _{el} is the terminal phase rate constant calculated by a linear regression of the log-linear concentration timecurve.

a if data permit; sd: single dose; ss: steady-state

CCI

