 To confirm PF-06952229 safety profile in combination with enzalutamide at the estimated RP2D in patients with mCRPC. To estimate efficacy of PF-06952229 in combination with enzalutamide at the estimated RP2D in patients with mCRPC. To confirm the RP2D of PF-06952229 in combination with enzalutamide in patients with mCRPC. 	 AEs as graded by NCI CTCAE version 5.0. Laboratory abnormalities as graded by NCI CTCAE version 5.0. PSA50 Response Rate. Response assessment will be based on PCWG2 and RECIST 1.1.
Secondary Objective(s):	Secondary Endpoint(s):
 To estimate additional efficacy of PF-06952229 at the estimated RP2D in patients with mCRPC. To further evaluate the PK of PF-06952229 when given in combination with enzalutamide. To evaluate immune cells in paired pre and post treatment tumor biopsies (where available). 	 ORR based on PCWG2 and RECIST 1.1. and time to event endpoints (DoR, PFS, OS, TTP, TTR). Pharmacokinetic parameters of PF-06952229 (in at least 8 subjects). Single Dose (SD) - C_{max}, T_{max}, AUC_{last}, and as data permit, AUC_{inf}, CL/F, V_z/F, and t_{1/2}. Multiple Dose (MD) - C_{ss,max}, T_{ss,max}, AUC_{last}, C_{ss,min}, and as data permit CL_{ss}/F, V_{ss}/F, t_{1/2}, and R_{ac} (AUC_{last}/AUC_{last}). Peak and trough concentrations at selected cycles. Assessment of levels of intra-tumor T cells (eg, CD8 IHC);

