9.4. Analysis of Pharmacokinetics CCl

9.4.1. Analysis of Pharmacokinetics

9.4.1.1. Single-Dose and Steady-State PF-06952229 Pharmacokinetic Analysis

Plasma PK parameters including the maximum plasma concentration (C_{max}), time to maximum plasma concentration (T_{max}), and area under the plasma concentration versus time curve (AUC_{last}) for PF-06952229 will be estimated using noncompartmental analysis. If data permit or if considered appropriate, area under the plasma concentration versus time curve from time 0 extrapolated to infinity (AUC_{inf}), terminal elimination half-life ($t_{1/2}$), apparent oral plasma clearance (CL/F), apparent volume of distribution (V_{ss} /F or V_z /F), accumulation ratio (R_{ac}) and linearity ratio (R_{ss}) will be also estimated. The single-dose and steady-state PK parameters will be summarized descriptively (n, mean, standard deviation, coefficient of variation [CV], median, minimum, maximum, geometric mean and its associated CV) by dose, cycle and day.

For PF-06952229 concentrations, concentrations will be summarized descriptively (n, mean, standard deviation, CV, median, minimum, maximum, geometric mean and its associated

CV) by dose, cycle, day and nominal time. Individual patient and median profiles of the concentration-time data will be plotted by dose, cycle and day (single dose and steady state) using nominal times. Individual and median profiles will be presented on both linear-linear and log-linear scales.

Dose normalized AUC_{last} and C_{max} will be plotted against dose (using a logarithmic scale) by cycle and day. These plots will include individual patient values and the geometric means for each dose. These plots will be used to help understand the relationship between the PK parameters and dose.

The observed accumulation ratio and the linearity ratio will be summarized descriptively. Each will be analyzed after natural log transformation using a one-way analysis of variance (ANOVA) with a single term for dose. The means and 90% confidence intervals (CIs) obtained from the model will be back-transformed to provide means and 90% CIs for the accumulation and linearity ratios for each dose.

Trough concentrations will be plotted for each dose using a box-whisker plot by cycle and day within cycle in order to assess the attainment of steady state.

Urine PK parameters (Ae%, CL_R) for PF-06952229 will also be estimated and summarized.

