5.4.3. Pharmacokinetics

Concentrations below the limit of quantification

In all data presentations (except listings), concentrations below the limit of quantification (BLQ) will be set to zero. (In listings BLQ values will be reported as “<LLQ”, where LLQ (ie, lower limit of quantification) will be replaced with the value for the LLQ).

Deviations, missing concentrations and anomalous values

Patients who experience events that may affect their PK (eg, incomplete dosing) may be excluded from the PK analysis.

In summary tables and plots of median profiles, statistics will be calculated with concentrations set to missing if one of the following cases is true:

1. A concentration has been reported as ND (ie, not done) or NS (ie, no sample),
2. A deviation in sampling time is of sufficient concern or a concentration has been flagged anomalous by the pharmacokineticist.

Note that summary statistics will not be presented at a particular time point if more than 50% of the data are missing.

An anomalous concentration value is one that, after verification of bioanalytical validity, is grossly inconsistent with other concentration data from the same individual or from other subjects. For example, a BLQ concentration that is between quantifiable values from the same dose is considered as anomalous. Anomalous concentration values may be excluded from PK analysis at the discretion of the PK analyst.

Pharmacokinetic parameters

Actual PK sampling times will be used in the derivation of PK parameters. If a PK parameter cannot be derived from a subject's concentration data, the parameter will be coded as NC (ie, not calculated). (Note that NC values will not be generated beyond the day that a subject discontinues).

In summary tables, statistics will not be presented for a particular treatment group if more than 50% of the data are NC. For statistical analyses, PK parameters coded as NC will also be set to missing.

If an individual subject has a known biased estimate of a PK parameter, this will be footnoted in summary tables and will not be included in the calculation of summary statistics or statistical analyses.

CCI

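### SAP 6.3.2 assigns PK parameters only to dose-escalation patients, against SAP 3.2 and the protocol, and leaves trough undefined by day

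*SAP*

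**What the plan says.** SAP 6.3.2 has four relevant statements.

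- Parameters: "For patients enrolled in the dose escalation stage of the study, the individual concentration-time data of PF-06952229 during Cycle 1 and Cycle 2" are to be analysed by non-compartmental methods, with results summarised by dose level and cycle.
- Expansion: "For patients enrolled in Part 2 of the study, trough concentrations of PF-06952229 will be summarized descriptively by cycle and by tumor type".
- Profile plots: median curves are planned "for the concentration-time data after the 1st (C1D1) and 7th dose (C1D7", with all cohorts on one plot.
- Concentrations: these are summarised "according to dosing cohort and time for each part of the study".

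SAP 5.4.3 adds that, outside listings, "concentrations below the limit of quantification (BLQ) will be set to zero". SAP 3.2 lists the full single-dose (SD) and multiple-dose (MD) parameter set under a heading that covers both Part 1 and Part 2.

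Protocol Section 2 makes the SD and MD parameters secondary endpoints of Part 2A. It does the same for Part 2B, in at least 8 subjects, and adds "Peak and trough concentrations at selected cycles". Protocol 9.4.1.1 summarises parameters by dose, cycle and day with no restriction by part. It shows troughs by cycle and by day within the cycle, "in order to assess the attainment of steady state".

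**The concern.** The section that tells the programmers what to compute does not name Parts 2A and 2B in its parameter paragraph. Serial samples are nevertheless scheduled there for that purpose. Part 2B exposure matters in particular: protocol 1.2.4 predicts a 70% fall in AUC with enzalutamide, and protocol 5.7.1 asks patients in Parts 1B and 2B who start on a proton-pump inhibitor to keep it unchanged until after the Cycle 2 Day 1 visit, so that the effect of enzalutamide on exposure can be estimated.

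The second issue is the missing day. With 7 days on and 7 days off, a predose sample can be an on-drug trough, a pre-treatment blank or a washout value, depending on the day. A summary by cycle alone does not separate them. If they were mixed, the table would show low troughs in Cycles 1 and 2 and an apparent rise at Cycle 3, where only Day 7 is sampled.

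**Working it through.** **1. Endpoints, schedules and the SAP text side by side**

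| Part | PK endpoints, protocol Section 2 | Serial profiles to 12 h | SAP 6.3.2 parameter paragraph |
|---|---|---|---|
| 1A | SD and MD parameters | C1D1, C1D7, C2D1 | covered |
| 1B | SD and MD parameters | C1D1, C1D21, C2D1 | covered |
| 2A | SD and MD parameters | C1D1, C1D7 | not named; troughs only |
| 2B | SD and MD parameters (at least 8 subjects), peak and trough | C1D1, C1D21, C2D1 (at least the first 8 patients) | not named; troughs only |

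A concentration summary for every part does not yield AUC, CL/F, half-life or accumulation ratio.

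**2. Half-life.** Protocol 1.2.4 predicts CL 5 mL/min/kg and Vss 3 L/kg. ln 2 × 3000 / 5 = 416 min = 6.93 h, which reproduces the stated value of about 7 h.

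**3. Time since last dose.** Take morning dosing on Day 1 as time 0. The last dose of the first dosing week is the evening of Day 7, at 156 h.

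- C1D15 predose is at 336 h, so 336 − 156 = 180 h after the last dose. C2D1 has the same gap after the Day 21 evening dose.
- C2D10 is at 216 h of its cycle, so 60 h after the last dose, or 36 h if drawn at the end of its −24 h window.
- C1D1 predose is before any drug.

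**4. Size relative to the 12-h on-drug trough.** Assume one-compartment decay with k = ln 2 / 7 = 0.099 per h. The ratio is exp(−k(T − 12)).

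- T = 180 h: 6 × 10⁻⁸.
- T = 60 h: 0.009. T = 36 h: 0.093.
- Part 2B Day 2 (24 h after the single Day 1 dose): exp(−12k) × (1 − exp(−12k)) = 0.305 × 0.695 = 0.21.

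**5. Cycle means if every predose sample were pooled**

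- Part 2A Cycle 1 (D1, D7, D15): (0 + 1 + 0)/3 = 0.33. Without C1D1: (1 + 0)/2 = 0.50.
- Part 2A Cycle 2 (D1, D7, D10): (0 + 1 + 0.009)/3 = 0.34, or (0 + 1 + 0.093)/3 = 0.36 with an early D10.
- Part 2B, intensively sampled, Cycle 1 (D1, D2, D7, D15, D21): (0 + 0.21 + 1 + 0 + 1)/5 = 0.44.
- Part 2B, intensively sampled, Cycle 2 (D1, D2, D7, D10): (0 + 0.21 + 1 + 0.009)/4 = 0.31.
- Cycle 3 onward (D7 only): 1.00.

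Over half-lives of 4 to 20 h, Part 2A Cycle 1 stays at 0.33 and Cycle 2 lies between 0.33 and 0.40 (0.34 to 0.48 with an early D10). Part 2B is 0.42 to 0.45 in Cycle 1 and 0.28 to 0.35 in Cycle 2. With unquantifiable values set to zero, a geometric mean of such a pool would be zero or undefined.

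**6. The plotted day.** On C1D7, Part 1B has a predose sample only and Part 2B has predose and 2 h, so neither has a full profile. Nor is C1D7 the 7th dose. Twice-daily dosing on Days 1 to 6 gives 12 doses, so the Day 7 morning dose is the 13th in Parts 1A and 2A. It is the 12th in Parts 1B and 2B, where Day 1 carries a single dose.

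**The case against.** The strongest reply is that a reader might infer that the Part 2 PK endpoints have been dropped, and the documents do not say that. SAP 3.2 keeps them for both parts, the parameter-method table in 6.3.2 is not limited to escalation, and protocol 9.4.1.1 has no restriction by part. Text after the table is also blacked out and cannot be judged. This stands: what can be shown is a contradiction, not a decision to omit. The contradiction does not settle itself, though. Protocol Section 9 lets the SAP modify what the protocol outlines, and it requires an amendment only for major changes to primary endpoints or their analysis. The narrower text in 6.3.2 could therefore be followed.

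A reader might also infer that washout samples will be averaged in as troughs. No sentence says so. The schedules call them predose samples, and few analysts would call a pre-drug C1D1 value a trough. The ratios above are therefore the size of an error that the wording permits, not one that it orders.

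Similarly, summarising parameters by dose level and cycle might be read as pooling the Day 1 and steady-state values. The SAP's method table separates single-dose from steady-state results, and the accumulation ratio needs both, so separation is implied. The day should still be stated, as in the protocol.

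The 7-h half-life is a prediction without enzalutamide, so its use for Part 2B is uncertain. The conclusion changes little from 4 to 20 h. The dose-number slip and the reference to tumor type are minor on their own.

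**Conclusion.** SAP 6.3.2 is wrong as written. Its parameter paragraph and its Part 2 sentence conflict with SAP 3.2 and with protocol Sections 2 and 9.4.1.1. The secondary SD and MD parameters of Parts 2A and 2B, and the Part 2B peak, are left without a stated analysis in that section. It also loses the day from two summaries, leaves trough undefined, and names a multiple-dose profile day that does not fit Parts 1B and 2B.

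If all predose samples were pooled by cycle, Part 2A means in Cycles 1 and 2 would be 0.33 to 0.36 of the on-drug trough (0.50 in Cycle 1 without C1D1). For intensively sampled Part 2B patients they would be 0.31 to 0.44. These figures assume one-compartment decay, a half-life of about 7 h, doses 12 h apart, and equal on-drug troughs on Days 7 and 21, which induction by enzalutamide could disturb.

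The analyses are descriptive, SAP 5.1 states no hypotheses, and no data are lost. The matter is one of correct and complete reporting of secondary endpoints.

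**What to change.** Revise SAP 6.3.2 as follows.

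- (a) Extend the non-compartmental paragraph to Part 2A and to at least the first 8 patients of Part 2B, and add the Part 2B peak and trough summaries.
- (b) Summarise parameters and troughs by dose, cycle and day, as protocol 9.4.1.1 does.
- (c) Name C1D7 as the multiple-dose profile in Parts 1A and 2A and C1D21 in Parts 1B and 2B, and remove the reference to the 7th dose.
- (d) Define trough as the predose sample on Day 7, and on Day 21 where collected. List the other predose samples separately.
- (e) Delete the split by tumor type for Part 2, where every patient has mCRPC.
- (f) Vss/F is given as "CL * MRT, where MRT is the mean residence time adjusted for the duration of infusion", but PF-06952229 is a tablet. Remove the infusion wording, then either correct the formula for oral dosing or document the parameter's removal consistently with the protocol, which lists it as an endpoint.

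Steady state should not be judged by comparing the predose and 12-h samples of one profile unless actual sampling times are used. The 12-h sample has a −180 min window, and at a 7-h half-life a 9-h value is 2^(3/7) = 1.35 times the 12-h value even at true steady state.

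The cost is SAP wording and some programming. No new samples are needed.
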